10.7. Safety Review

Treatment-related toxicity is the safety end point.

All patients who received at least one dose of orteronel and who had at least one post baseline safety assessment will be evaluated for toxicity. Patients enrolled, but never treated, will not be included in any of the safety analyses. The actual dose and duration in days of orteronel as well as the dose intensity will be listed and summarized by descriptive statistics. Assessment of safety will be based on the frequency of AEs and on the number of laboratory events that fall outside of predetermined ranges as assessed by the investigator. The incidence of treatment-emergent AEs will be summarized by system organ class, severity (NCI CTCAE, Version 4.0), type of AE, and relationship to study drug. Any other pertinent information collected will be listed, as appropriate.

Observed levels and changes from baseline will be examined for the following hormones at scheduled time point assessments (baseline, at Cycle 2 Day 1, Cycle 3 Day 1, and at the End-of-Treatment Visit): serum estradiol, total and free testosterone, SHBG, ACTH, DHEA-S, and cortisol.

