 - Alanine aminotransferase (ALT) and aspartate aminotransferase (AST) $\leq 2.5 \times$ the upper limit of normal (ULN), if no liver involvement or $\leq 5 \times$ ULN with liver involvement
 - Total bilirubin ≤ 1.5 times the upper limit of normal (ULN) (in patients with known Gilbert Syndrome, a total bilirubin $\leq 3.0 \times$ ULN, with direct bilirubin $\leq 1.5 \times$ ULN)
10. Adequate renal function, defined as:
 - Creatinine $\leq 1.5 \times$ ULN or creatinine clearance $\geq 40 \text{ mL/min}$, as calculated by the Cockcroft-Gault method
11. Screening calculated LVEF of $\geq 50\%$ by echocardiogram (ECHO) or by multiple-gated acquisition (MUGA) scan
12. Ability to swallow and retain oral medication
13. Male patients, even post vasectomy, who are willing to use adequate contraceptive measures (see Appendix B) or abstain from heterosexual intercourse during the entire study treatment period and for 4 months after the last dose of study drug
14. Female patients who are not of child-bearing potential and female patients of child-bearing potential who agree to use adequate contraceptive measures (see Appendix B) or abstain from heterosexual intercourse during the entire study treatment period and for 4 months after the last dose of study drug, who are not breastfeeding, and who have had a negative serum/urine pregnancy test ≤ 7 days prior to dosing
15. Life expectancy of ≥ 3 months
16. Willingness and ability to understand the nature of this study and to comply with the study and follow-up procedures.

CONFIDENTIAL

STUDY DRUG: Orteronel

SCRI INNOVATIONS STUDY NUMBER: BRE 203

DATE OF PROTOCOL: Version 3.0 30 October 2013

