6.1.3. Dose Modifications Due to Non-Hematologic Toxicity

Due to its mechanism of action, treatment with orteronel may elicit expression of adverse reactions typically associated with androgen deprivation. Risks associated with androgen deprivation include hot flushes, decreased libido, loss of energy, QTc interval prolongation, or mood swings. Long-term effects of testosterone suppression may also occur, including effects on bone mineral density, muscle mass, hyperglycemia, or lipid or energy metabolism.

Adverse events commonly recorded during clinical trials with orteronel include fatigue, nausea and vomiting, rash, and worsening hypertension. Pancreatitis and/or elevated amylase/lipase have also been reported, occurring in <5% of patients in studies conducted with orteronel.

CONFIDENTIAL

STUDY DRUG: Orteronel

SCRI INNOVATIONS STUDY NUMBER: BRE 203

DATE OF PROTOCOL: Version 3.0 30 October 2013

Pancreatic enzymes will be measured during scheduled serum chemistries for patients receiving long-term administration of orteronel.

For fatigue, mild or intermittent nausea and vomiting, or rash, dose modifications of orteronel should follow the guidelines in Section 6.1.1, depending on the severity.

For \geq Grade 3 QTc interval prolongation (QTcF >500 ms or >60 ms change from baseline on at least two separate ECGs), orteronel should be held until recovery to \leq Grade 1 (<480 ms). The patient's chemistries should be checked, as well as concomitant medication usage. Once QTc interval prolongation has resolved, orteronel may be restarted at the reduced dose level. For a second occurrence of \geq Grade 3 QTc interval prolongation, orteronel should be discontinued.

In the event of any grade 4 non-hematologic toxicity, orteronel should be discontinued.

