6.1.3.8. Abnormal Liver Function Tests

The incidence of liver function abnormalities is expected to be low. Grade 2 or 3 abnormal liver function tests (LFTs) that are considered by the investigator to be possibly related to orteronel administration should be managed as appropriate, using Table 11 as a guide. A decision to re-challenge and/or resume dosing at a lower dose should be reviewed with the Monitor in all cases.

CONFIDENTIAL

STUDY DRUG: Orteronel

SCRI INNOVATIONS STUDY NUMBER: BRE 203

DATE OF PROTOCOL: Version 3.0 30 October 2013

Table 11 Management of Abnormal AST and ALT Bearing a \geq Possible Relationship to Orteronel Treatment

AST and/or ALT Elevation Grade (per NCI CTCAE)	Concurrent Bilirubin Level	Required Orteronel Dose Modification
Grade 1	$\geq 1.5 \times$ ULN	Hold until bilirubin resolves to $<1.5 \times$ ULN Reduce dose to 200 mg BID, if receiving 300 mg BID, otherwise discontinue orteronel
Grade 2	$<1.5 \times$ ULN	Hold until ALT/AST resolve to Grade 1 Reduce dose to 200 mg BID, if receiving 300 mg BID, otherwise discontinue orteronel
Grade 2	$\geq 1.5 \times$ ULN	Discontinue orteronel
Grade 3/4	Any	Discontinue orteronel

Note: Following orteronel dose de-escalation due to AST/ALT and/or bilirubin abnormalities, no re-escalation is permitted.

Abbreviations: ALT = alanine aminotransferase; AST = aspartate aminotransferase; BID = twice daily; NCI CTCAE = National Cancer Institute Common Terminology Criteria for Adverse Events; ULN = upper limit of normal

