7.4.1. Day 1 of Each Cycle

The following assessments will be performed on Day 1 of each cycle:

- Medical history
- Physical examination including measurements of weight and vital signs (resting heart rate, blood pressure, respiratory rate, and oral temperature) (**weekly during Cycle 1 for Lead-in patients**)
- ECOG performance status
- AE assessment (**weekly during Cycle 1 for Lead-in patients**)
- Concomitant medication review (**weekly during Cycle 1 for Lead-in patients**)
- CBC, including 3-part differential and platelets (Day 1 of each cycle ± 3 days) (**weekly during Cycle 1 for Lead-in patients**)(need not be done on Cycle 1 Day 1 if baseline was taken within 72 hours of that day)

CONFIDENTIAL

STUDY DRUG: Orteronel

SCRI INNOVATIONS STUDY NUMBER: BRE 203

DATE OF PROTOCOL: Version 3.0 30 October 2013

- CMP (Day 1 of each cycle \pm 3 days) (**weekly during Cycle 1 for Lead-in patients**) (need not be done on Cycle 1 Day 1 if baseline was taken within 72 hours of that day)
- Serum hormone levels: estradiol, total and free testosterone, SHBG, ACTH, DHEA-S, and cortisol (**Day 1 of Cycles 2, 4 and End of Treatment only** [see Section 7.5])
- Serum amylase/lipase
- Serum/urine pregnancy test (for women of childbearing potential only). If the baseline reading was done within 72 hours of Cycle 1 Day 1, this test need not be repeated on that day.
- Study drug compliance assessment

7.4.2. Day 1 of Cycle 3 and Every Other Cycle Following (Cycles 5, 7, 9, etc), except where noted

- Fasting plasma glucose, insulin, c-peptide, and HbA_{1c} (only in patients with a history of diabetes)
- 12-lead ECG
- CT scan of the chest /abdomen/pelvis (only those scans abnormal at baseline need to be repeated)
- Bone scan (if clinically indicated)
- CT/MRI of the brain (if clinically indicated)

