7.6.3. Comprehensive Metabolic Profile

The following laboratory tests should be performed for each patient for assessment of CMP:

- glucose
- blood urea nitrogen (BUN)
- creatinine
- sodium
- potassium
- chloride
- calcium
- carbon dioxide (CO₂)
- alkaline phosphatase (ALP)
- AST
- ALT
- total bilirubin
- total protein

CONFIDENTIAL

STUDY DRUG: Orteronel

SCRI INNOVATIONS STUDY NUMBER: BRE 203

DATE OF PROTOCOL: Version 3.0 30 October 2013

- albumin

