10.5. Statistical Analyses

All statistical analyses will be performed using SAS 9.1.3 or the current version of SAS available at the time of analysis.

In general, data will be listed and/or summarized and tabulated. Descriptive statistics, such as means, median, standard deviation, minimum and maximum for continuous variables, and counts and percentages for discrete variables, will be used to summarize data as appropriate.

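### Section 10.7 counts out-of-range laboratory events without reference to baseline, so the planned count mixes abnormality at entry with low-grade worsening on orteronel

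*Combined protocol and SAP*

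**What the plan says.** Section 10.7 bases the safety assessment on the frequency of AEs and "on the number of laboratory events that fall outside of predetermined ranges as assessed by the investigator". The ranges are not given there or elsewhere. Section 6 adopts CTCAE v4.0 for grading toxicity and Section 13.2 asks sites for their laboratory normal ranges, but neither is tied to this count. Nor is the counting unit stated: it could be the patient, the test or the individual result.

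The same section does use baseline for one group of tests: "Observed levels and changes from baseline will be examined for the following hormones at scheduled time point assessments". That list covers estradiol, testosterone, SHBG, ACTH, DHEA-S and cortisol. CBC, CMP, amylase and lipase are not on it.

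Section 10.5 adds a general provision: "Descriptive statistics, such as means, median, standard deviation, minimum and maximum for continuous variables". It does not mention change from baseline or worst grade.

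Section 11.4.3 decides which laboratory values become AEs: every Grade 3 or 4 value, and Grade 1 or 2 values only if clinically significant. Section 11.4.6 makes a pre-existing condition an AE only if it worsens. That rule governs AE and SAE recording, not the laboratory count.

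**The concern.** All patients receive orteronel, so each patient's own baseline is the only comparator in the trial. A patient who enters with raised ALT and stays there is out of range at every visit. So is a patient who enters normal and rises to the same level on drug. A count of out-of-range events treats the two alike, and if results rather than patients are counted, a stable abnormality is counted again at each cycle.

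Safety and tolerability is a secondary objective, and Section 1.3 says orteronel had not been investigated in AR+ metastatic breast cancer. Three laboratory signals that the protocol itself links to the drug could sit in this count without a baseline:

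- **Liver.** Hepatotoxicity is an identified risk in Section 1.2.2.1.
- **Mineralocorticoid effect.** Section 6.1.3.4 names low potassium and raised sodium as possible indicators.
- **Pancreas.** Section 6.1.3 states: "Pancreatitis and/or elevated amylase/lipase have also been reported, occurring in <5% of patients in studies conducted with orteronel".

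**Working it through.** The plan states no figure for the laboratory summary, so there is none to reproduce. The check sets the sections side by side.

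**Step 1. What entry admits (Section 3.1, items 8 to 10).** ALT/AST up to 2.5 × ULN, or 5 × with liver involvement; bilirubin up to 1.5 × ULN, or 3.0 × in Gilbert syndrome; creatinine up to 1.5 × ULN or clearance of at least 40 mL/min; hemoglobin down to 9 g/dL; platelets down to 75 × 10⁹/L. Section 7.6.3 lists 14 CMP tests. Four (ALT, AST, total bilirubin, creatinine) have an entry limit for all patients, leaving 14 − 4 = 10 without one. One of the ten is glucose, which exclusion 16 restricts only in patients with diabetes. Item 7 requires recovery to Grade 1 or better from clinically significant toxicity of prior therapy, which still admits Grade 1.

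**Step 2. What is left to the count alone.**

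| Laboratory change | Where else it is picked up | Left to the count? |
|---|---|---|
| Any Grade 3/4 | AE under 11.4.3, then the treatment-emergent table in 10.7 | No |
| Grade 1/2, clinically significant | Same | No |
| Grade 1/2 hematologic toxicity | 6.1.2: hold and re-evaluate in 1 week; dose intensity summarised in 10.7 | Largely no |
| Grade 1/2 creatinine | Table 10: largely graded against baseline; evaluation at Grade 1, hold at Grade 2 | Largely no |
| Grade 1/2 glucose | Table 6: HbA1c check at both grades, reassessment at Grade 2 | Largely no |
| Possibly related Grade 2 ALT/AST, or Grade 1 with bilirubin ≥1.5 × ULN | Table 11: dose action | No |
| Grade 1 ALT/AST, bilirubin <1.5 × ULN | No row in Table 11 | Yes |
| Mild potassium or sodium drift without hypertension | 6.1.3.4 applies to new or worsening hypertension with potassium <3.5 mEq/L | Yes |
| Grade 1/2 amylase or lipase | Measured on Day 1 of each cycle (7.4.1); no management table | Yes |

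Check on Table 11: 3 ALT/AST levels (Grade 1, 2, 3/4) × 2 bilirubin levels = 6 combinations. The rows cover 1 + 1 + 1 + 2 = 5, since the Grade 3/4 row applies at any bilirubin. The sixth is isolated Grade 1.

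**Step 3. How the count behaves.** For one test, let b be the proportion out of range at entry and remaining so, and e the proportion of the others who become abnormal on treatment. The share of flagged patients who were abnormal at entry is b / (b + (1 − b)e). The documents give neither b nor e, so the values below are assumptions.

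- b = 0.10, e = 0.20: 0.10 / (0.10 + 0.18) = 36%.
- b = 0.20, e = 0.10: 0.20 / (0.20 + 0.08) = 71%.
- b = 0.40, e = 0.05: 0.40 / (0.40 + 0.03) = 93%.

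The width of this range shows only that the count cannot be interpreted without b. It does not estimate b.

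**The case against.** The strongest reply is that the plan already captures what matters clinically. Serious and clinically significant values go to a treatment-emergent table. Low-grade hematologic, creatinine and glucose changes trigger management, and creatinine is already judged largely against baseline. ACTH and cortisol have change from baseline. What remains is mild, untreated drift that the investigator judged unimportant. A missing row for isolated Grade 1 ALT/AST in a dose-modification table is also reasonable where entry allows 2.5 × ULN; it is not itself an analysis defect. All of this stands, and it sets the size of the point.

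It could also be said that investigator assessment in Section 10.7 lets the investigator discount abnormality known at entry. The text does not say so, and a count that depends on an unwritten discount could not be reproduced.

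A reader might infer more than the documents support:

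- **That worsening cannot be separated from entry abnormality at all.** Not so. CBC, CMP, amylase and lipase are taken at screening, on Day 1 of each cycle and at end of treatment (Sections 7.3, 7.4.1, 7.5), and Section 10.5 allows listings. The fault is in the planned count, not in the data.
- **That 10 of 14 tests, or 1 of 6 Table 11 combinations, measures harm.** These figures describe coverage. They say nothing about how many patients are affected.
- **That 36% to 93% of flagged patients would be misattributed.** Those figures rest wholly on assumed rates.

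**Conclusion.** The point holds in limited form. Followed as written, Section 10.7 yields a laboratory count that mixes entry abnormality with on-treatment worsening, in a trial with no control arm and with entry limits that admit out-of-range values.

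Its reach is the descriptive summary of Grade 1/2 changes not called clinically significant, notably isolated Grade 1 ALT/AST, mild potassium or sodium drift, and amylase/lipase. This assumes that sites apply Section 11.4.3 and the dose-management sections as written. Response, disease control and the Section 10.4 decision rules are untouched. No misattribution rate is claimed, because the documents do not say how many patients enter out of range.

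It is a cheap improvement, and more than a request for missing detail: a better summary exists for data already collected.

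**What to change.** Keep the treatment-emergent AE table. Replace the laboratory count in Section 10.7 with:

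> For CBC parameters, ALT, AST, ALP, total bilirubin, potassium, sodium, calcium, albumin, amylase and lipase, baseline CTCAE v4.0 grade will be cross-tabulated against worst on-treatment grade, with the number and percentage of patients (each counted once per test) whose grade worsened, by cohort. Creatinine will be summarised as the maximum on-treatment ratio to baseline using the Table 10 categories. Potassium and sodium will also be summarised as change from baseline.

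Three choices need explaining:

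- **Creatinine is handled separately** because Table 10 grades it mostly relative to baseline, so a cross-tabulation by baseline grade would say little.
- **Glucose should be graded only where fasting values exist.** Table 6 defines Grades 1 and 2 on fasting glucose; fasting samples are specified only for patients with a history of diabetes (Sections 7.3, 7.4.2), and CMP glucose is not stated to be fasting.
- **Urinalysis is left out.** It is taken only at screening and end of treatment, and no orteronel signal is argued for it.

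No visits, samples or patients are added. The cost is a few extra tables. Grades based on ULN also need each site's laboratory limits, at about 15 sites. Section 13.2 collects normal ranges as start-up documents, but nothing says that they are entered in the eCRF, so capturing them may be additional work.

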2.2. Secondary Objectives

The secondary objectives of this study are to evaluate:

- Safety and tolerability of the regimen
- Measurement of changes in serum estradiol levels, total and free testosterone levels, and sex hormone binding globulin (SHBG) during treatment with orteronel
- Measurement of changes in ACTH, DHEA-S, and cortisol levels during treatment with orteronel
- Progression-free survival (PFS)
- Overall survival (OS)

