3. STUDY PATIENT POPULATION AND WITHDRAWAL

This study will enroll patients with MBC who have progressed on prior hormonal/ chemotherapy regimens and whose cancer expresses AR. Patients will be enrolled onto one of the 2 following cohorts based on their tumor specificity:

- Cohort 1: Patients with estrogen receptor negative (ER-)/ progesterone receptor negative (PR-)/ human epidermal growth factor receptor 2 negative (HER2-)/AR positive (+) MBC with 1 to 3 previous treatments for metastatic disease
- Cohort 2: Postmenopausal women with ER+ and/or PR+/AR+ refractory MBC who have progressed after at least one, and up to 3, previous hormonal treatments for metastatic disease.

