3.1. Inclusion Criteria

Patients must meet the following criteria in order to be included in this clinical study:

1. Voluntary written informed consent before performance of any study-related procedure not part of normal medical care
2. Patients must have MBC that is measurable or evaluable as defined by Response Evaluation Criteria in Solid Tumors (RECIST) v1.1 criteria (see Section 9). Patients with metastases limited to the bones are eligible.
3. Patients with breast tumors that are AR+ (>10% staining by immunohistochemistry). Archived tumor tissue from a primary biopsy or metastatic lesion for centralized determination of AR expression is mandatory. If tissue is limited, the additional correlative testing is optional. If tissue is not available, a patient will not be eligible for enrollment into the study. Patients may enroll based on local laboratory AR assessment, but will need to submit tissue for confirmation at the central laboratory.
4. In addition to having AR+ tumors, patients must fit into 1 of the 2 following categories:
 - Triple negative (ER-/PR-/HER2-) *Note: This group of patients must have received at least 1 and up to 3 prior chemotherapy regimens in the advanced setting.*
 - ER+ and/or PR+ *Note: This group of postmenopausal patients must have received at least 1 and up to 3 prior hormonal therapies and at least one prior chemotherapy treatment in the advanced setting. HER2+ patients in this group must have received a minimum of 2 lines of HER2-directed therapy in the advanced setting.* This group of patients may be pre-menopausal with ovarian suppression or post-menopausal. LHRH agonists maybe used to render ovarian suppression with post-menopausal ranges of estradiol or FSH per institutional guidelines.
5. Female or male patients ≥ 18 years-of-age

CONFIDENTIAL

STUDY DRUG: Orteronel

SCRI INNOVATIONS STUDY NUMBER: BRE 203

DATE OF PROTOCOL: Version 3.0 30 October 2013

6. Eastern Cooperative Oncology Group (ECOG) performance status score of 0, 1, or 2 (see Appendix A)
7. Patient has recovered (to Grade ≤ 1) from all clinically significant toxicities related to prior antineoplastic therapies (with the exception of alopecia)
8. Adequate hematological function, defined as:
 - Absolute neutrophil count (ANC) $\geq 1.25 \times 10^9/L$
 - Platelets $\geq 75 \times 10^9/L$
 - Hemoglobin $\geq 9 \text{ g/dL}$
9. Adequate liver function, defined as:

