5. STUDY DESIGN

This is an open-label, multicenter, Phase II study to be conducted in 2 stages. All patients will receive orteronel PO at a dose of 300 mg twice daily (BID) (600 mg total daily dose).

- Lead-in Phase: The first 6 patients treated will be evaluated every week to confirm the safety and feasibility of this regimen. After all 6 patients complete at least 4 weeks of treatment, and if no prohibitive toxicities are identified, continuous study treatment will begin.
- Continuous Study Treatment: Patients will continue to be enrolled into both cohorts based on their tumor specificities up to a total of 31 patients in Cohort 1 (ER-/PR-/HER2-/AR+) and 55 patients in Cohort 2 (ER+ and/or PR+/AR+). These numbers include the patients that are participating in the lead-in phase.

Up to 86 patients are planned to be enrolled in this study (6 for the lead-in phase and 80 for continuous study treatment).

Patients will be evaluated every eight weeks for response to treatment.

All patients who respond to treatment (complete response [CR] or partial response [PR]) or have stable disease (SD) will continue to receive orteronel until they develop progressive disease (PD) or unacceptable toxicity.

The study design schema is presented in Figure 1.

[figure not shown]
CONFIDENTIAL

STUDY DRUG: Orteronel

SCRI INNOVATIONS STUDY NUMBER: BRE 203

DATE OF PROTOCOL: Version 3.0 30 October 2013

Figure 1. BRE 203 Treatment Schema

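### Hormone changes in Section 10.7 have no relative scale and no split by sex or menopausal status, so a pooled mean change and its SD could mislead

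*Combined protocol and SAP*

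**What the plan says.** Section 2.2 makes hormone change a secondary objective: "Measurement of changes in serum estradiol levels, total and free testosterone levels, and sex hormone binding globulin (SHBG) during treatment with orteronel", with a parallel item for ACTH, DHEA-S and cortisol. The analysis is one sentence in Section 10.7, "Observed levels and changes from baseline will be examined for the following hormones at scheduled time point assessments", followed by seven analytes. It names no statistic, scale, interval or subgroup. Section 10.5 supplies the general rule, to be applied as appropriate: "Descriptive statistics, such as means, median, standard deviation, minimum and maximum for continuous variables".

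On who contributes data:

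- Section 3.1, item 5 admits "Female or male patients ≥ 18 years-of-age". No cap on men and no expected number is given.
- Section 3.1, item 4, on the receptor-positive group (Cohort 2): "This group of patients may be pre-menopausal with ovarian suppression or post-menopausal". The next sentence refers to ovarian suppression with estradiol or FSH in the postmenopausal range.
- Section 3.1, item 4, on the triple-negative group (Cohort 1): "This group of patients must have received at least 1 and up to 3 prior chemotherapy regimens in the advanced setting". No menopausal or suppression condition is attached, and item 14 admits women of child-bearing potential.
- The opening of Section 3 describes the second cohort differently: "Cohort 2: Postmenopausal women with ER+ and/or PR+/AR+ refractory MBC".

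Section 5 plans 31 patients in Cohort 1 and 55 in Cohort 2, 86 in all.

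**The concern.** The study's hypothesis (Section 1.1) is that tumours may respond when androgen levels are lowered, and Section 1.3 says the drug has not been studied in AR-positive metastatic breast cancer. The other correlative work uses archived tissue, so the serial hormone samples are the only on-treatment evidence that the drug does what it is meant to do in these patients.

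The question they should answer is relative: by what fraction does each hormone fall or rise? A difference from baseline does not answer it when baselines differ widely. If men and women are pooled, or women with and without ovarian function, the arithmetic mean change gives most weight to the patients with the highest baselines, and the SD grows with them. A reader could take the pooled mean as the typical change in women when a few other patients supply much of it.

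**Working it through.** The plan states no expected change, SD or precision for any hormone, so there is no figure to reproduce. The check is a sensitivity calculation for testosterone.

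**Inputs.** From Section 5: n = 31, 55 or 86. Assumed, because the documents give no figure: k = 1 or 2 men, and a male-to-female ratio of baseline testosterone R between 5 and 30.

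**Step 1: men's share of the pooled mean change.** Set the women's baseline to 1 and the men's to R, and let everyone fall by the same fraction f. The total fall is f(kR + n − k), of which the men supply fkR. Their share is kR / (kR + n − k), whatever f is.

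| n | Men | R = 5 | R = 10 | R = 20 | R = 30 |
|---|---|---|---|---|---|
| 31 (Cohort 1) | 1 | 14% | 25% | 40% | 50% |
| 31 | 2 | 26% | 41% | 58% | 67% |
| 55 (Cohort 2) | 1 | 8% | 16% | 27% | 36% |
| 55 | 2 | 16% | 27% | 43% | 53% |
| 86 (both) | 1 | 6% | 11% | 19% | 26% |
| 86 | 2 | 11% | 19% | 32% | 42% |

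The ends of the range are 5/(5 + 85) = 6% and 60/(60 + 29) = 67%. Fewer patients will have samples at later visits, so n there will be smaller and the share of any man still sampled larger.

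**Step 2: which statistics are affected.** Simulation with 3,000 runs per case. Further assumptions: baseline log-SD 0.6, median fall 50%, log-SD of the change 0.4. Units are the median female baseline; R = 20.

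| n | Men | Mean change | SD of change | Median change | Geometric mean ratio |
|---|---|---|---|---|---|
| 31 | 0 | −0.55 | 0.47 | −0.45 | 0.50 |
| 31 | 2 | −1.23 | 3.10 | −0.48 | 0.50 |
| 55 | 0 | −0.55 | 0.47 | −0.45 | 0.50 |
| 55 | 2 | −0.93 | 2.36 | −0.47 | 0.50 |
| 86 | 0 | −0.55 | 0.48 | −0.45 | 0.50 |
| 86 | 2 | −0.79 | 1.91 | −0.46 | 0.50 |

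The formula agrees: the mean is multiplied by (kR + n − k)/n, which for n = 31 is 69/31 = 2.23, and −0.55 × 2.23 = −1.23. With R = 5 and two men among 31, the mean is −0.69, the SD 0.85 and the median −0.48. So the mean and SD move, the median barely moves, and the geometric mean ratio does not move.

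**Step 3: why a split by sex is needed as well as a ratio.** Steps 1 and 2 assume the same relative fall in both sexes. As an extreme, suppose women do not change and men fall by 80%. With two men among 31 and R = 20, the pooled mean change divided by the pooled mean baseline is 0.8 × 40/69 = 46%, although no woman changed. A pooled geometric mean ratio would be 0.2^(2/31) = 0.90, still an apparent 10% fall. Only a summary for women alone shows no change.

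**Step 4: menopausal status.** In Cohort 2, item 4 ties ovarian suppression to postmenopausal ranges of estradiol or FSH, so its suppressed women are meant to resemble the postmenopausal ones. In Cohort 1 nothing excludes premenopausal women without suppression. Mixing by menopausal status is therefore mainly a Cohort 1 matter, and mainly one for estradiol. The documents give no figures from which to size it.

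**Step 5: visits.** Section 10.7 analyses baseline, Cycle 2 Day 1, Cycle 3 Day 1 and end of treatment. Sections 5.2.1 and 7.4.1 and Appendix E schedule the samples at baseline, Cycle 2 Day 1, Cycle 4 Day 1 and end of treatment. One planned analysis visit has no scheduled sample, and one scheduled sample has no planned analysis.

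**The case against.** The best defence is that Section 10.5 already contains much of the remedy. It lists the median, minimum and maximum beside the mean and SD, applies them as appropriate, and allows data to be listed. The median hardly moves with one or two men, and the minimum or maximum would expose them. This stands, and it limits the point to the mean and SD. It does not close the gap: no statistic is named as the one that answers the objective, and a median of absolute changes still does not give relative suppression.

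Three stronger readings are tempting and are not supported:

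- *The plan has chosen raw arithmetic mean changes.* A plain difference is the natural reading of a change from baseline, but Section 10.7 does not exclude a percent or log change. The fair criticism is that the scale is unspecified.
- *One or two men will drive the testosterone result.* No number of men is expected or stated, no hormone levels are given, and the opening of Section 3 describes Cohort 2 as women only, which conflicts with items 4 and 5 of Section 3.1. At R = 5 the men's share is only 6% to 26%.
- *Ovarian-suppressed women in Cohort 2 are on a different estradiol scale.* Item 4 points the other way.

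It is also true that nothing turns on this analysis formally: the stopping and success rules in Section 10.4 use response alone. Nor do the documents say that suppression is proportional or that every analyte should fall; Section 1.2.2.1 lists compensatory ACTH elevation as a risk. A ratio to baseline describes a rise as well as a fall, but proposing one requires a rule for values below the assay limit.

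**Conclusion.** The point holds in a limited form and is a minor improvement. For a secondary objective in a population of mixed sex and, in Cohort 1, possibly mixed ovarian function, the plan fixes no relative scale, no interval and no split. A pooled mean change and its SD could be distorted by a few patients with high baselines; the median would not be, to any important degree.

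The size is conditional. With one or two men and a testosterone ratio of 5 to 30, all assumed, men supply about 6% to 67% of the pooled mean change. They supply more than half only with two men and a high ratio in a single cohort; one man among 31 at R = 30 supplies exactly half. If no men enrol, that part disappears. What remains is that absolute changes do not measure relative suppression and that Cohort 1 may mix premenopausal women without suppression with others. The mismatch of Cycle 3 and Cycle 4 is a plain inconsistency and depends on no assumption.

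**What to change.** In Section 10.7:

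- For each hormone and each sampled visit, report the ratio to baseline for women by cohort, as a geometric mean ratio with 95% CI.
- State in advance how values below the assay limit are handled, report how many there are, and use the median percent change where they are many, with the cut-off for that set beforehand.
- List men individually.
- For estradiol, show Cohort 1 premenopausal women without ovarian suppression separately where numbers allow.
- Keep raw medians and ranges as support.
- Reconcile the visit list with Sections 5.2.1 and 7.4.1 and Appendix E.

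The description of Cohort 2 at the start of Section 3 and items 4 and 5 of Section 3.1 should also be reconciled, so that the groups to be reported are clear.

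The cost is a few sentences and some extra table rows. The scheduled samples suffice. The subgroups will be small and their intervals wide, so they should be read as description only.
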